1.0 INTRODUCTION

External Beam Radiation Therapy in the Management of Clinically Localized Prostate Cancer: Rationale for Dose Escalation

Local tumor control with radiation is dose-dependent, following a sigmoid dose-response relationship. Results of early clinical applications of conventional external-beam radiation treatment (60–70 Gy in 2-Gy fractions) yielded 10-year disease-free survivals ranging from 40%–70% prompting investigations of dose escalation (1-6). The randomized dose escalation trial performed at the M. D. Anderson Cancer Center compared 70 Gy to 78 Gy (7). As expected, the 78-Gy arm resulted in improved local control, but, at the price of increased rectal complications. Similar results have been obtained in other reported randomized trials (8-9). The risk of rectal bleeding appears to be dependent on both the radiation dose and the volume of the rectum subjected to high doses (10-12).

It has become clear that increases in the total dose delivered to the prostate enhance local tumor control, offering a therapeutic benefit, as long as normal tissue tolerances are respected. Intensity modulated radiation therapy (IMRT) is considered a dosimetric improvement over 3DCRT. Dosimetric comparisons of conventional treatment plans with IMRT plans have revealed that IMRT is capable of sparing adjacent normal tissues (13, 14). Use of IMRT for prostate cancer treatment allows for high levels of clinical and biochemical local control with lower complication rates as compared to conventional external-beam techniques (14, 15).

Rational for Hypofractionation

The optimal radiation schedule for the curative treatment of prostate cancer remains unknown. Prostate cancer patients receiving IMRT are typically treated 5 days per week for 8-9 weeks. This prolonged treatment time is inconvenient for many patients and increases treatment costs. Recent data suggest that large radiation fraction sizes are radio-biologically favorable over lower fraction sizes in prostate cancer radiotherapy (16). The sensitivity of a tumor or normal tissue to fraction size of radiation can be approximated by the alpha-beta ratio (α/β). Recently, Brenner and Hall (17) suggested that the α/β for prostate cancer is actually as low as 1.5. These results imply that the current radiation therapy paradigm for prostate cancer treatment might be fundamentally flawed, as high fraction sizes would be expected to damage tumor more readily. These findings are of considerable interest for prostate cancer treatment and could be exploited with high fraction-size radiation therapy.

Stereotactic Body Radiation Therapy In the Management of Prostate Cancer

The term stereotactic refers to precise positioning which safely allows higher radiation doses per fraction and fewer fractions (hypofractionation) than conventional RT. Multiple single institution experiences suggest high biochemical control rates with acceptable toxicity (18-24).

These series suggest that clinically significant late Grade 3 toxicities are infrequent and lower or similar to rates observed in series of IMRT patients. Early quality of life data indicate that treatment is well tolerated with acceptable declines in patient reported urinary, bowel and sexual function (25). Recent updates have confirmed a 5-10 year biochemical disease-free survival in excess of 90% and local control greater than 98% (26-28). The use of SBRT has accelerated in the last few years largely due to early efficacy and safety data and high degree of penetration of IMRT techniques in the radiation oncology community. As such, the learning curve associated with SBRT compared to IMRT is not as steep. A survey of 500 radiation oncologists in 2010 found that approximately 64% had reported using SBRT in their practice for some type of cancer (29). Second, the number of SBRT-capable radiation platforms has expanded significantly since the introduction of CyberKnife SBRT in 1999. Additionally, cost is also significantly less for SBRT compared to IMRT or proton therapy and this has become increasingly important with scarce healthcare dollars (30).

Clinical Experience with Hypofractionation for Unfavorable Clinically Localized Prostate Cancer

Large radiation fraction sizes have been clinically utilized in the treatment of unfavorable prostate cancer for many years. HDR brachytherapy as a boost to external-beam radiotherapy (EBRT) has shown promise in this regard (31-36). Initial trials combined external beam radiation therapy (36-50.4 Gy) with high dose rate (HDR) brachytherapy (2-4 fractions of 3-11.5 Gy). HDR brachytherapy was employed to escalate the dose to gross disease within the prostate and seminal vesicles. HDR brachytherapy allows greater flexibility in dose delivery which provides for intraprostatic dose escalation and optimization of periprostatic doses. Supplemental EBRT was designed to treat the prostate and seminal vesicles with a margin to encompass adjacent microscopic disease. Draw backs relate to associated hospitalization with the patient confined to bed and remaining supine for 24-48 hours to accommodate treatment. Even so, catheter migration between treatments is common and must be corrected (36-38).

Similarly, recent long term data from the ASCEND-RT trial utilizing LDR brachytherapy boost in similar fashion showed a dramatic 21% improvement in biochemical control at 9 years favoring LDR brachytherapy boost compared to conventional dose escalated EBRT although no corresponding benefit was identified in overall survival, incidence of bone metastases or prostate cancer specific mortality (39). Unfortunately, the incidence of late grade 3 or higher urinary toxicity was increased 3-fold (18 vs 6%) in the LDR brachytherapy arm compared to the EBRT arm. Given the associated toxicity and resources with brachytherapy boosts, recent research has focused on utilizing prostate SBRT to deliver escalated doses similar to HDR or LDR brachytherapy since SBRT is well tolerated and non-invasive (42-43).

Radiation Dose Selection

In this protocol, CK-SBRT will be used to target the microscopic and gross disease in the prostate, seminal vesicles. An escalated dose of 40Gy in 5 fractions will be delivered to the entire target volume while any nodules visible within the prostate gland on endorectal MRI will receive 50Gy in 5 fractions. The linear quadratic formula was used to calculate equivalent doses and three assumptions were made: 1) Sublethal damage is completely repaired between fractions, 2)

No repair of sublethal damage occurs during a given fraction, and 3) No repopulation occurs during the treatment course (i.e., there is no time factor). Data analysis from grouped prostate hypofractionation trials (1) suggests that an EQD_2 of > 80 Gy may be required to achieve long term biochemical disease free survival in the 96-98% range. In this protocol, this dose will be achieved by five SBRT treatments (Minimum EQD_2 108.6 Gy calculated 3 mm from the prostate border). The feasibility and safety of DE-SBRT for treating localized prostate cancer has been shown in two recently completed prospective trials (44). These studies confirm that DE-SBRT is technically feasible and reproducible with acceptable toxicity similar to or lower than patients receiving DE-IMRT.

Evaluating Quality of Life After the Treatment of Prostate Cancer.

The treatment alternatives for clinically localized prostate cancer provide similar local control and survival (46). Quality of life (QOL) outcomes are thus an important factor in selecting treatment (47). Several studies have demonstrated that radiation treatment for prostate cancer can adversely affect urinary, bowel and sexual function (25, 26). The severity and duration of these toxicities varies among patients. The expanded prostate cancer index composite (EPIC) has been developed as a disease specific, patient-administered instrument to measure quality of life in men with prostate cancer (48). Thus, acceptance of a novel regimen for treatment of unfavorable-risk prostate cancer patients must not only be effective and have minimal impact on short- and long-term quality of life, but it must also be cost effective (30,49). Quality-Adjusted Life Years (QALYs) are well-established for measurement of cost-effectiveness for many different types of diseases, and can be calculated through use of clinical quality of life measurements, such as the EuroQol EQ-5D (50). These tools will be utilized for longitudinal QOL assessments for the duration this study.

The Philadelphia CyberKnife Experience

The Philadelphia CyberKnife center is a highly specialized radiation oncology facility within the Crozer Keystone Health System with a sole focus on stereotactic radiation therapy services and delivery. As one of the early adopters and pioneers of SBRT techniques, our expertise and experience is on par with nationally renowned academic centers and our physicians serve on national committees and lead multi-institution prospective trials. Our published experience with CyberKnife prostate SBRT has shown favorable biochemical control compared to IMRT cohorts with low toxicity rates (51, 52). We have also compared prostate SBRT to IMRT using a large national database showing no detriment to SBRT compared to IMRT (53, 54). We will leverage our experience, expertise and national standing to conduct this pivotal prospective study.

Updated Clinical Experience for SBRT

Since initiation of the current trial two important randomized studies have been published which support the current trial structure and importance. Focal boost to the intraprostatic MRI documented tumor has been studied in a recently completed randomized Phase III trial for external beam radiotherapy with standard IMRT 77Gy/35 fractions (2.2Gy per fraction) vs same dose to the prostate with integrated focal boost up to 95Gy (2.7Gy per fraction). The recently completed trial published January 2021 coined the FLAME trial revealed an improvement of biochemical disease free survival for patients with intermediate and high risk prostate cancer

with integrated boost without impacting toxicity and quality of life. (56) More importantly, a phase III trial (HYPO-RT-PC) of 1200 men with intermediate to high risk prostate cancer found ultra-hypofractionation 42.7Gy/7fx to be non-inferior to conventional fractionation 78Gy/39fx with late toxicity similar in both treatment arms. (57) The National Comprehensive Cancer Network (NCCN) version 4.2022 defines SBRT as an acceptable standard radiation treatment option for unfavorable, high and very high risk prostate cancer using 5 fractions with dose of 36.25-40Gy, www.nccn.org. Therefore, the experimental aspect of this research is the additional boost to MRI defined nodule with dose painting.

Defining Unfavorable Risk Prostate Carcinoma

For this study, 3 sub-classifications of unfavorable risk prostate carcinoma will be defined.

1. Unfavorable Intermediate Risk Carcinoma: Any patients with intermediate risk prostate cancer not meeting favorable risk classification.
 - a. Gleason score 4+3=7
 - b. Gleason score 3+4=7 with more than 50% of cores positive
 - c. Gleason Score 3+4=7 and PSA 10-20 ng/ml
 - d. Gleason Score 3+4=7 and >T2a
2. High Risk Prostate Cancer:
 - a. T3a (ECE only) or
 - b. Gleason score 8 or
 - c. PSA >20 ng/ml
3. Very High Risk Prostate Cancer:
 - a. T3b or
 - b. Gleason Score 9-10 or
 - c. PSA >20 ng/ml

STUDY SCHEMA

1. Registration
2. Endorectal/Multi parametric MRI and Staging Studies
3. Ultrasound with fiducial and SPACE OAR placement
4. Planning CT and MRI
5. SBRT treatment to the prostate and proximal seminal vesicles (4000 cGy in 5 treatments)

PATIENT ELIGIBILITY

Histologically confirmed adenocarcinoma of the prostate diagnosed within 360 days of enrollment.

PSA documented within 90 days prior to registration.

Clinical staging completed within 90 days of registration.

No Nodal or Distant Metastases documented on CT or MRI of the pelvis and bone scan (PSMA PET/CT may be substituted for bone scan).

Unfavorable Risk Prostate Carcinoma as Described is documented.

No prior pelvic radiotherapy.

No prior TURP.

Prostate volume < 100 cc

AUA score < 20

No recent (within 5 years) or concurrent cancers other than non-melanoma skin cancers.

Patient must have no medical or psychiatric illnesses that would interfere with treatment or follow-up.

No implanted hardware adjacent to the prostate that would prohibit appropriate treatment planning and treatment delivery is allowed.

Patient must speak and comprehend the English language to complete questionnaires.

Patient's with very high risk prostate cancer must be seen in consultation by medical oncology as per NCCN guidelines version 4.2022 for consideration for abiraterone or docetaxel following radiation.

ELIGIBILITY CHECKLIST

(Y) 1. Is there histologically confirmed adenocarcinoma of the prostate within 360 days of enrollment?

2. What is the Gleason score?

3. What is the T stage?

(N0 or Nx) 4. What is the N stage?

(M0 or Mx) 5. What is the M stage?

(ng/ml) 6. What is the PSA (< 90 days prior to registration)?

(N) 7. Has the patient had prior pelvic radiation?

(N) 8. Has the patient had a TURP?

(< 100 cc) 9. Is the prostate volume < 100 cc?

(N) 10. Has the patient had previous (within the last 5 years) or concurrent cancer other than basal cell or squamous cell skin cancer?

(N) 11. Are there any major medical or psychiatric illnesses which would prevent the completion of treatment or interfere with follow-up?

(Y) 12. Has the patient signed a study-specific consent form?

(AUA < 20) 13. Is the patient's AUA score < 20?

(N) 14. Does the patient have implanted hardware adjacent to the prostate that would prohibit appropriate treatment planning and treatment delivery?

2.0 OBJECTIVES

This is a phase II study designed to prospectively evaluate the efficacy and safety of DE CK-SBRT for unfavorable risk prostate cancer in a community setting.

Hypothesis

1. Dose Escalated Stereotactic Body Radiation Therapy is adequate for biochemical control of Unfavorable Intermediate and High Risk Prostate Cancer.

Primary Objective

1. To assess efficacy endpoints: Biochemical disease-free survival (bDFS) assessed using the Phoenix definition (55), duration of local control, distant failure and site of distant failure, disease-free survival, disease-specific survival and overall survival.

Secondary Objectives

1. To estimate the proportion of patients who develop late (> six months) grade 3-5 gastrointestinal and genitourinary toxicity observed following SBRT for prostate cancer.
2. To evaluate Quality of life (QOL) using standardized instruments.

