Quality-Adjusted Life Years (QALY): **EuroQol EQ-5D-5L** is a validated instrument which provides a single index value for a patient’s overall health status (otherwise known as “utility”). It is widely used in cancer clinical trials (56, 57). Five of the items are scored on a 3-point Likert scale (mobility, ability for self-care, ability to perform usual activities, pain/discomfort, anxiety/depression), and one item assesses a patient’s overall health state on a visual analog scale ranging from 0 (worse imaginable state) to 100 (best imaginable).

8. STATISTICAL CONSIDERATIONS:

Endpoints:

Primary Endpoint

1. **Toxicity** will be assessed using the NCI Common Toxicity Criteria version 4.0.

Secondary Endpoints

1. **Biochemical disease-free survival (bDFS)** will be defined as the time in months from completion of SBRT to biochemical failure. Patients who are free from biochemical failure on the date of closing follow-up will be censored on that date. The Phoenix definition will be used to assess biochemical failure as described in Section 10.
2. **Duration of local control** will be defined as the time in months from SBRT completion to local failure.
3. **Distant failure (includes regional failure)** will be defined as the time in months from SBRT completion to distant failure.
4. **Disease-free survival** will be defined as the time in months from the date that the patient is determined to be free of disease to the date of known disease recurrence for any measure of disease. Patients who are alive and free from disease recurrence on the date of closing follow-up will be censored on that date.
5. **Disease-specific survival** will be defined as the time in months from completion of SBRT to death due to prostate cancer, other causes with active malignancy, or complications from treatment. Patients who are alive or dead with disease relapse but with inactive disease on the date of closing will be censored on that date.
6. **Overall survival** will be defined as the time in months from SBRT completion until death. Patients who are alive on the date of closing will be censored on that date.
7. **Quality of life**

Study Design:

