The target sample size is 100 patients for this Phase II study. Allowing for a 15% ineligibility rate, the total sample size is 115 patients. Accrual is anticipated to be completed within 5 years of institutional IRB approval. This Phase II trial will provide information to guide future Phase III studies. Sample size determination is based on the late toxicity endpoint. A single-stage Fleming design will be used to test the null hypothesis that the late unacceptable radiation toxicity probability at 2 years p is < 0.05 versus the alternative hypothesis that toxicity probability at 2 years is > 0.15 . Unacceptable toxicity will be defined as grade 3 or higher toxicity. If 10 or fewer patients experience late radiation toxicities at 2 years, the null hypothesis will not be rejected and then the regimen will be considered for a phase III study. If at least 10 patients experience late radiation toxicities at 2 years, the null hypothesis will be rejected. This design has a power of 89% and a type I error rate of 0.10.

Analysis Plan

1. Number and percentage of subjects for each toxicity will be summarized overall by body system and by onset time (acute: ≤ 90 days of treatment start and late: >90 days of treatment start). The tabulation will also be separated by toxicities of Grade 3 and above.
Future studies incorporating DE-SBRT would be worthwhile if the rate of grade 3 GU/GI toxicity was $\leq 10\%$.
2. Biochemical disease-free survival, disease-free survival, disease-specific and overall survival curves will be calculated and presented by the methods of Kaplan and Meier.
3. The proportion of patients with local and distant failure will be reported with a 95% binomial confidence interval.
4. General health related and disease specific quality of life measurements will be summarized over time. Graphical displays will be created for each patient's trajectory over time and also summarized using the average for all patients.

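### Section 2 makes efficacy the primary objective, Section 8 makes toxicity the only primary endpoint, and the biochemical-control hypothesis has no criterion

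*Protocol*

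**What the plan says.** Section 2 (Objectives) states one hypothesis: "Dose Escalated Stereotactic Body Radiation Therapy is adequate for biochemical control of Unfavorable Intermediate and High Risk Prostate Cancer". Its single primary objective is "To assess efficacy endpoints: Biochemical disease-free survival (bDFS) assessed using the Phoenix definition (55), duration of local control, distant failure", and it continues through "distant failure and site of distant failure, disease-free survival, disease-specific survival and overall survival". Toxicity comes under the secondary objectives: "To estimate the proportion of patients who develop late (> six months) grade 3-5 gastrointestinal and genitourinary toxicity".

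Section 8 (Statistical Considerations) has one entry under Primary Endpoint, toxicity, which "will be assessed using the NCI Common Toxicity Criteria version 4.0". bDFS heads the secondary endpoints and "will be defined as the time in months from completion of SBRT to biochemical failure". Local control, distant failure, disease-free survival, disease-specific survival, overall survival and quality of life follow it.

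Under Study Design, "Sample size determination is based on the late toxicity endpoint". A single-stage Fleming design with a target of 100 patients tests a 2-year late radiation toxicity probability below 0.05 against one above 0.15, and "Unacceptable toxicity will be defined as grade 3 or higher toxicity". With 10 or fewer events the null stands and the regimen is considered for phase III; with at least 10 events the null is rejected. The stated power is 89% and the stated type I error 0.10.

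The Analysis Plan adds a second criterion for going on, a grade 3 GU/GI rate of at most 10%. For efficacy it gives Kaplan-Meier curves, and binomial 95% intervals for local and distant failure.

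**The concern.** An endpoint should measure the objective of the same rank. Here the primary endpoint serves a secondary objective, and the primary objective is served only by secondary endpoints. Section 1 (Updated Clinical Experience for SBRT) shows that the trial has started, and Section 7 has PSA and toxicity recorded at follow-up visits in a single-arm study. While the protocol supports either outcome as primary, the emphasis could be settled after results are known.

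The hypothesis in Section 2 also cannot be confirmed or refuted as written. It turns on the word adequate, and no rate or rule gives that word a meaning.

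**Working it through.** **1. The two sections side by side**

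| Item | Section 2 | Section 8 |
|---|---|---|
| Hypothesis | Biochemical control is adequate | Late toxicity below 0.05 versus above 0.15 at 2 years |
| Efficacy (bDFS, local control, distant failure, DFS, DSS, OS) | Primary objective | Secondary endpoints 1 to 6 |
| Toxicity | Secondary objective, estimation | Only primary endpoint, formal test |
| Sample size | Not addressed | Late toxicity |
| Criteria for further study | None | Two, both on toxicity |
| Late means | More than six months | More than 90 days from treatment start (as in Section 7) |
| Organ scope | GI and GU | No organ limit in the test; GU/GI in the 10% criterion |

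Nothing in the protocol reconciles the two columns.

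**2. Is there a criterion for adequate control?** Section 1 mentions 5-10 year bDFS above 90% in earlier series, and long-term bDFS of 96-98% when justifying the dose. Both are background; neither is adopted as a reference for this trial. bDFS itself is defined (Phoenix rule, time origin, censoring). What is missing is the criterion.

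As an illustration, assume 90 of 100 patients free of biochemical failure and no censoring. The exact (Clopper-Pearson) 95% interval is 82.4% to 95.1%. That is a usable estimate, but the protocol does not say whether it would be adequate.

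What 100 patients can deliver depends on the missing benchmark. For an assumed one-sided exact test at the 5% level with no censoring, power is 0.44 for 90% versus 95%, 0.88 for 80% versus 90%, and 0.94 for 85% versus 95%.

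**3. The toxicity test as stated.** Inputs from Section 8: N = 100, p0 = 0.05, p1 = 0.15, stated type I error 0.10, stated power 0.89. For rejection at r or more events,

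P(X ≥ r | p) = Σ (k = r to 100) C(100, k) p^k (1 − p)^(100 − k),

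which is the type I error at p = 0.05 and the power at p = 0.15.

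| Reject at | Type I error | Power |
|---|---|---|
| ≥ 8 | 0.128 | 0.988 |
| ≥ 9 | 0.063 | 0.973 |
| ≥ 10 | 0.028 | 0.945 |
| ≥ 11 | 0.012 | 0.901 |

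The stated power is approximately reproduced at 11 or more (0.901 against 0.89). The stated 0.10 is not the attained level of either cutoff that the text supports.

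**4. The overlap at exactly 10 events.** The probability of exactly 10 events in 100 is 0.017 at a true rate of 5%, 0.132 at 10% and 0.044 at 15%. The first and last are the differences between the two rules: 0.0282 − 0.0115 = 0.0167 and 0.9449 − 0.9006 = 0.0443. The chance of missing a 15% rate is 1 − 0.945 = 0.055 with the lower cutoff and 1 − 0.901 = 0.099 with the higher.

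**The case against.** The strongest reply is that Section 8 is the operative design. It sizes and tests on toxicity, efficacy estimation is normal in phase II, and an analysis plan that is not shown may hold the detail. The opening sentence of Section 2 names efficacy and safety together, so joint objectives may have been meant. Part of this stands: descriptive efficacy analysis is legitimate, and a time point for reading a Kaplan-Meier curve is often left to the analysis plan, so its absence alone is not a finding. But an analysis plan cannot make two protocol sections agree on what is primary. The joint reading does not help either, because Section 2 goes on to rank efficacy as primary and toxicity as secondary.

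It is also fair that exact binomial tests seldom hit a nominal level. Read as a ceiling, 0.10 is met at 9, 10 or 11 events. The point on type I error is therefore one of reporting, not of an inflated error rate.

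A reader might infer several stronger things that the documents do not support:

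- *That rejecting at 11 or more is the only rule consistent with the text.* It fits both the 10-or-fewer sentence and the 10% criterion only with exactly 100 evaluable patients. With 115, 11 events is 11/115 = 9.6%, rejected yet within 10%. With 98, 10 events is 10/98 = 10.2%, not rejected yet above 10%. The 10% criterion also covers GU/GI toxicity only, and the higher cutoff is the weaker one for detecting excess toxicity.
- *That the test counts grade 3 or higher events of any cause.* Section 8 speaks of late radiation toxicity, so the gap from GI/GU is one of organ scope only.
- *That site of distant failure was dropped.* Section 8 does not list it, but Section 7 has the type of metastatic failure recorded if known.
- *That the primary was switched after data were seen.* The text shows that this is possible, not that it happened.

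**Conclusion.** The contradiction stands and needs no calculation. All six efficacy outcomes are primary in Section 2 and secondary in Section 8; toxicity moves the other way. No efficacy measure has a reference rate or decision rule, so adequate biochemical control cannot be judged. This must be fixed, because it decides what the trial reports as its main result.

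The linked defects in the toxicity endpoint are real but smaller: two definitions of late, two organ scopes, and opposite decisions at exactly 10 events. Choosing between the two cutoffs moves type I error between 0.028 and 0.012 and power between 0.945 and 0.901. These figures assume 100 evaluable patients, each with known 2-year status, and independent binomial outcomes. The efficacy interval and powers in the working are illustrations on assumed rates.

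**What to change.** Issue a dated amendment that names one primary, aligns Sections 2 and 8, and discloses which toxicity and PSA data had been seen by then.

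- **Route that keeps the present sizing.** Make late grade 3 or higher radiation toxicity at 2 years the primary objective and hypothesis. List the efficacy measures as secondary, described as estimation with 95% confidence intervals.
- **If bDFS is to be primary.** Section 8 must state a reference rate, a time point and a decision rule for it, and say what 100 patients can deliver against them.

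In the same amendment:

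- Use one definition of late and one organ scope throughout Sections 2, 7 and 8.
- Reconcile the two sentences that conflict at exactly 10 events, and restate type I error and power for the cutoff chosen. The choice is the sponsor's, made knowing that 11 or more is less likely than 10 or more to detect a 15% toxicity rate.

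The cost is an amendment and its review, with no new patients or data on the toxicity route; efficacy claims become descriptive. The bDFS route costs more, because the present sample size was not derived for it.

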6.0 PATIENT ASSESSMENTS

| Assessment | Pre-entry | | | | Follow-up interval: months post therapy | | | | |
|----------------------------|-----------|---|---|---|---|----|----|-------|---|
| | | 1 | 3 | 6 | 12 | 18 | 24 | 36-60 | |
| History (SHIM, AUA) | X | | X | X | X | X | X | | X |
| Physical exam (DRE) | X | | | X | X | X | X | | X |
| ECOG Performance Scale | X | | | X | X | X | X | | X |
| Prostate Biopsy | X | | | | | | | | |
| PSA | X | | | X | X | X | X | | X |
| Prostate volume assessment | X | | | | | | | | |
| Bone scan | X | | | | | | | | |
| Pelvic imaging | X | | | | | | | | |
| Toxicity evaluation (AUA) | X | | X | X | X | X | X | | X |
| EPIC-26 Questionnaire | X | | | | X | X | | X | X |
| EuroQol EQ-5D-5L | X | | | | X | X | | X | X |

Assessment schedule: Quality of life measurements will take place per the table, then annually through 5 years post-treatment.

7.0 CLINICAL ENDPOINTS:

Patients will have toxicity evaluation weekly during treatment. At 1 month following treatment, patients will be assessed for acute toxicity. At 6, 12, 18, and 24 month intervals (and every year thereafter, through year 5- 10, if investigators opt to continue past year 5), patients will be seen and evaluated, including a history, physical exam, performance status, PSA, toxicity evaluation. In addition, at 6 months, 12 months and annually thereafter, EPIC-26 will be administered. Examination and studies may be done at outside facility. Prostate biopsy, bone scan (PSMA PET/CT may be substituted for bone scan) and pelvic MRI will be performed at time of biochemical or clinical failure.

Criteria for toxicity:

Acute side effects (<=90 days of treatment start) and late side effects (> 90 days of treatment start) will be assessed using the NCI Common Toxicity Criteria version 4.0 (see appendix V).

Criteria for disease control:

1. Biochemical disease free survival (bDFS):
 - a. Phoenix definition (55): failure occurs when the PSA is ≥ 2 ng/ml more than the lowest PSA measurement before the current one, with no backdating. Administration of salvage therapy will be considered failure.

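### Late toxicity starts after six months in the Section 2 objective but after 90 days from treatment start in Sections 7 and 8, so the same patients can yield two late rates

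*Protocol*

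**What the plan says.** Three places in the protocol give late toxicity a cut-off.

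- Section 2.0 Objectives, secondary objective 1: "To estimate the proportion of patients who develop late (> six months) grade 3-5 gastrointestinal and genitourinary toxicity observed following SBRT".
- Section 7.0 Clinical Endpoints, criteria for toxicity: "late side effects (> 90 days of treatment start".
- Section 8 Statistical Considerations, Analysis Plan item 1, on how toxicities are tabulated: "by onset time (acute: ≤ 90 days of treatment start and late: >90 days of treatment start".

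Three further statements in Section 8 use the concept without giving a cut-off.

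- The single-stage decision rule counts late radiation toxicities at two years. On one side it reads "If 10 or fewer patients experience late radiation toxicities at 2 years, the null hypothesis will not be rejected", and on the other "If at least 10 patients experience late radiation toxicities at 2 years, the null hypothesis will be rejected".
- The event is qualified by grade only: "Unacceptable toxicity will be defined as grade 3 or higher toxicity".
- Analysis Plan item 1 adds a benchmark that begins "Future studies incorporating DE-SBRT would be worthwhile if the rate of grade 3 GU/GI toxicity was" and ends with a limit of 10%. It names organ systems but no time window.

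Section 8 lists toxicity as the primary endpoint and states that the sample size rests on the late toxicity endpoint.

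**The concern.** One term has two cut-offs, and they differ by about three months. The starting point may differ as well: Sections 7 and 8 count from treatment start, while Section 2 speaks only of toxicity following SBRT. With a course of 7 to 10 days, that second difference is small.

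This is not detail that can be left to a statistical analysis plan. The protocol states both definitions, so an analysis that follows one departs from the other. An event that starts between day 91 and six months also has no clear place under the Section 2 objective. It is too early to be late there, and too late to be acute under the only definition of acute that the protocol gives.

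At stake is the late grade 3 or higher rate, the quantity on which the trial is sized. If the choice is still open when events are classified, it can be made with the data in view, and one of the two options can only lower the reported rate.

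**Working it through.** **Step 1. The plan's own figures.** Section 8 gives n = 100, rates of 0.05 and 0.15, power 89% and type I error 0.10. With X ~ Bin(100, p):

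- Reject at 11 or more: P(X ≥ 11 | 0.05) = 0.0115 and P(X ≥ 11 | 0.15) = 0.9006.
- Reject at 10 or more: P(X ≥ 10 | 0.05) = 0.0282 and P(X ≥ 10 | 0.15) = 0.9449.

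The stated power is close to the first version. The stated type I error matches neither. That mismatch, and the assignment of a count of exactly 10 to both outcomes, are separate matters. The conflict of definitions does not depend on them, so both thresholds are carried below.

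**Step 2. Length of the disputed interval.** Inputs: SBRT lasts 7 to 10 days (Section 4.0), and a month is taken as 365.25/12 = 30.44 days.

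- Six months counted from the end of SBRT falls on day 7 + 182.6 = 189.6 to day 10 + 182.6 = 192.6 from treatment start. The interval after day 90 is 99.6 to 102.6 days.
- Two years from the end of SBRT falls on day 737.5 to 740.5, so the late window after day 90 is 647.5 to 650.5 days. The share is 99.6/647.5 = 15.4% to 102.6/650.5 = 15.8%.
- If six months and two years are both counted from treatment start, the share is (182.6 − 90)/(730.5 − 90) = 92.6/640.5 = 14.5%.

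**Step 3. Effect on the reported rate.** Let f be the share of late grade 3+ patients whose only such event starts in the disputed interval. The protocol gives no value for f, so it is an assumption here. A value of 15% is what onset spread evenly over the late window would give; 0%, 5% and 25% only show a range. All events are taken as GI or GU, to isolate the effect of timing. Then the six-month rate = the 90-day rate × (1 − f).

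| 90-day rate | f = 0 | f = 5% | f = 15% | f = 25% |
|---|---|---|---|---|
| 10% | 10% | 9.5% | 8.5% | 7.5% |
| 15% | 15% | 14.3% | 12.8% | 11.3% |

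Because f cannot be negative, the six-month rate is never the higher.

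**Step 4. Conditional illustration for the decision rule.** This applies only if the six-month cut-off were used in the rule. The six-month count cannot exceed the 90-day count, so for a rejection threshold c:

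P(decisions differ) = P(X ≥ c | p) − P(X ≥ c | p(1 − f))

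| True 90-day rate p | c | P(X ≥ c) | f = 5% | f = 15% | f = 25% |
|---|---|---|---|---|---|
| 0.05 | 11 | 0.0115 | 0.0035 | 0.0079 | 0.0101 |
| 0.10 | 11 | 0.417 | 0.065 | 0.188 | 0.288 |
| 0.15 | 11 | 0.901 | 0.041 | 0.157 | 0.322 |
| 0.05 | 10 | 0.0282 | 0.0075 | 0.018 | 0.0238 |
| 0.10 | 10 | 0.549 | 0.067 | 0.205 | 0.332 |
| 0.15 | 10 | 0.945 | 0.026 | 0.110 | 0.245 |

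With f = 0, or with the 90-day cut-off used throughout, every difference is zero.

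**The case against.** The strongest reply is that Section 7.0 holds the operative definition of late side effects, and that Section 8 repeats it just below the decision rule. A rule need not restate a term that is already defined. On this view the Section 2 wording is one stale parenthesis in a secondary objective, and nothing that matters turns on it. Most of this stands as far as the rule is concerned: more than 90 days is the natural reading there. It does not repair Section 2, which still asks for a different quantity under the same name.

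A second reply is that the two rates differ in scope anyway, because the Section 2 objective is limited to GI and GU events and the rule is not. That is correct, and it is why Step 3 takes all events as GI or GU. The timing gap remains within GI and GU events alone.

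A reader might infer from Step 4 that the go/no-go decision is unreliable in up to a third of trials. The documents do not support that. Those figures need the less likely reading of the rule, and the largest need f = 25%, which has no source in the protocol. At a true rate of 5% the difference is at most 1.0% (2.4% with rejection at 10).

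A reader might also infer from the row "Toxicity evaluation (AUA" in the Section 6.0 table that a month-3 toxicity visit is missing from the Section 7.0 text. The columns of that table, as available here, are out of register with their labels. The mark may belong to month 1, so no conclusion is drawn from it.

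**Conclusion.** The point holds as an internal inconsistency: the protocol is wrong as written, with minor to moderate severity. The firm consequence concerns reporting. Late grade 3 or higher GI/GU toxicity can be given as two different rates for the same patients, with events that start over about 93 to 103 days counted in one and not in the other. That conclusion rests on the running text alone. The size of the gap depends on f, which is unknown; at f = 15%, a 10% rate would be reported as 8.5%, and at f = 0 there is no gap.

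Any effect on the go/no-go decision is conditional. It arises only if the six-month cut-off is applied to the rule and the count lies near 10 or 11. The 10% GU/GI benchmark is less clear-cut: it shares the organ scope of the Section 2 objective, stands beside the 90-day tabulation, and states no window of its own.

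**What to change.** Change secondary objective 1 in Section 2.0 so that late means onset more than 90 days from treatment start, as in Section 7.0 and the Section 8 tabulation. In Section 8, name the same definition in the decision rule and in the 10% GU/GI criterion. This keeps the definition that already appears twice, and it is the more cautious choice for safety because it leaves no late event out.

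The cost is wording in Sections 2 and 8, with no added patients or visits. The downside is that the late rate reported for the Section 2 objective may be slightly higher, because events from day 91 to six months are then counted. The change is best made before late events are classified.
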